11.0 Risks

This research does not involve more than minimal risk to the participants as defined in SOP HRP-001 "Minimal Risk is the probability and magnitude of harm or discomfort anticipated in the research that are not greater in and of themselves than those ordinarily encountered in daily life or during the performance of routine physical or psychological examinations or tests." Engaging in regular moderate-

intensity PA and eating a healthy diet are not high risk activities. The education, active learning, goal-setting, and self-monitoring procedures employed in this study do not place the participants at risk for harm. There are some minimal risks associated with engaging in physical activity (e.g., sore muscles, dizziness, etc) that are no greater than those ordinarily encountered in daily life or during the performance of routine activity. Women with obstetric and medical complications and/or who meet the ACOG (2015) criteria for a contraindication to exercise will be excluded from study participation. There are no known risks of a mother eating a healthy diet and engaging in PA to the fetus. Most epidemiological data and the USDHHS (2008) guidelines illustrate benefits to the mother and the fetus such as improved stamina during delivery, lower rates of emergency C-sections, and reduced complications during delivery among healthy mothers. CRC nurses will check in during the exercise sessions during normal business hours. Trained fitness instructors with CPR training will be present at all times during the after-hours exercise sessions. If there should be a need for immediate medical care, assistance from the CRC would be solicited during normal business hours and after-hours, 911 would be called. A study staff member will also be present at all times during an exercise session. If immediate medical attention is needed, the study staff member will call 911, Penn State police and alert the PI.

There are no known economic, legal, or social risks associated with participation in this study. Some of the self-reported surveys may ask questions about your thoughts or feelings and make you feel uncomfortable, but they are not expected to cause feelings different from what is experienced in everyday life (e.g., completing a survey in a magazine or at the doctor's office). There are no risks associated with wearing activity monitors or using the breathing device for measuring metabolism. There are no risks associated with participating in the interview. Some discomfort may be experienced while in the BodPod if there is fear of small-enclosed spaces. The capsule has a window to see out of and to let light in. There is a blue button to press that will stop the measurement and let the participant out immediately. There are no risks to the women or child having a PeaPod measurement done. Mild nausea or dislike of food items may occur during the healthy eating demonstration due to normal pregnancy symptoms. There is a risk of loss of confidentiality if information or the participant's identity is obtained by someone other than the investigators, but precautions will be taken to prevent this from happening. See examples in the privacy section.

Some women experience minimal discomfort from the ultrasound scan. The sonographer may need to press firmly on the abdomen to get a clear image of the fetus. Having multiple ultrasound examinations during pregnancy does not result in negative short- or long-term effects on the physical or developmental growth of the baby. Official Statement on Safety in Training and Research Work (Approved, March 1997): "Diagnostic ultrasound has been in use since the late 1950's. There are no confirmed adverse biological effects on patients resulting from this usage. Although no hazard has been identified that would preclude the prudent and conservative use of diagnostic ultrasound in education and research, experience from normal diagnostic practice may or may not be relevant to the extended exposure times and altered exposure conditions. It is therefore considered appropriate to make the following recommendation: In those special situations in which examinations are to be carried out for purposes other than direct medical benefit to the individual being examined, the subject should be informed of the anticipated conditions, and how these compare with conditions for normal practice."

Blood draws may cause mild pain, swelling or bleeding. Participants may feel a small pinch or slight discomfort when the needle is inserted. If the initial blood draw is unsuccessful it may need to be repeated, with permission. There may be some bruising (blood under the surface of the skin), which can be minimized by pressing on the site after the needle is removed. There is also a slight chance of infection, dizziness or fainting. These risks will be minimized and most likely eliminated by having trained staff draw the blood in a clinical setting using sterile supplies. If dizziness or fainting occurs, the symptoms will be alleviated by having the woman lie flat with her feet raised. If these should occur, we may ask that the woman remain at the clinic until we have checked her blood pressure and we are sure that she feels well. Syringes used for venous blood draws will be used only once and then immediately discarded in a biohazardous waste container approved for sharps. Any staff member collecting or

processing blood will wear protective gloves at all times and will be training in safe techniques to minimize risk to the staff member.

Adverse events will be tracked and reported (see below in the DSMP section for more information) by the trained study staff with oversight from the CRC nurse. Safety-related events will be monitored and reported as required by the DSMP and the IRB. Intervention staff reporting and managing adverse events will inform the PI and in consultation with the study's Safety Officer, will determine if it is an unanticipated AE or unanticipated non-AE. Women with any health complications discovered at any time during the assessments will be referred for follow-up with their healthcare provider or given a list of local providers if they do not have a regular physician. Women who are not achieving appropriate GWG will be given the option to have a follow-up individual phone counseling session that week with the intervention facilitator to further discuss problem solving strategies. If any medical issues are uncovered that may be impacting their GWG, they will be referred to follow-up with their physician and Co-I, [name] will provide clinical consultation to determine if any changes to the intervention protocol should be made. See below for the monitoring plan for GWG in the DSMP section. Women in the intervention group who develop gestational diabetes during the study will receive the standard of prenatal care by their obstetrician or healthcare provider in which an established standard of care plan is provided for the treatment and management of gestational diabetes. The protocol for unexpected or adverse event during an exercise session is below:

I. REASONS FOR ACTION

Symptoms Checklist: Warning Signs to Stop Exercise (ACOG, 2015):

**Moderate to severe:
AND/OR:
RPE 15 or higher
exercise:**

Symptom Checklist	Pre	5-min	15-min	25-min	Post
Dizziness					
Nausea					
Headache					
Regular painful contractions					
Dyspnea before exercise					
Chest pain					
Calf pain or swelling					
Fluid leakage (urine or blood)					
Muscle weakness after exercise					

RPE

6	very, very light
7	very, very light
8	very light
9	very light
10	light
11	light
12	somewhat hard
13	somewhat hard
14	hard
15	hard
16	very hard
17	very hard
18	very, very hard
19	very, very hard
20	

during

II. ACTION

- STOP** activity
- Place participant in position of comfort.
- Call CRC if Monday-Friday (8 am – 5 pm) at [contact]. Send research assistant or staff person for help to CRC if needed (CRC is directly around the corner to the Left). Phone 911 if necessary.
- If the CRC is closed or no nurse is present, phone 911 if necessary.
- Notify participant's emergency contact person(s) as needed and/or per participant's request
- Call PI [name] [contact].
- Complete ORP significant event form (nurse or staff member).
- Report on study AE log (nurse or staff member).
- PI [name] need to submit a report to IRB within 5 weekdays; IRB determines if problems represent unanticipated problems that would potentially cause harm.
- See below for reporting AE and unanticipated problems.

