5. Baseline + Active Learning 4: Condition 1 description + adding 1 meal replacement (lunch or dinner) for 7 days, a fourth physical activity session with the choice of on site or at home and a weekly text/call/email feedback and encouragement for self-regulation/monitoring. The meal will be frozen meals, packaged for the week and they will meet the recommended dietary guidelines for pregnant women for lunch or dinner. The written scripts/handouts for these demonstrations are attached in the document section of CATS. The forms used to assess fidelity monitoring of these sessions are also attached in the documents section
6. Baseline + Active Learning 5: Condition 1 description + adding 1 meal replacement (lunch or dinner) for 7 days, a fourth physical activity session with the choice of on site or at home and text/call/email feedback and encouragement for self-regulation/monitoring 3x/week. The meal will be frozen meals, packaged for the week and they will meet the recommended dietary guidelines for pregnant women for lunch or dinner. The written scripts/handouts for these demonstrations are attached in the document section of CATS. The forms used to assess fidelity monitoring of these sessions are also attached in the documents section

After the follow-up assessment at gestational week 35, the participants will be followed through delivery and up to 6- weeks postpartum.

During the exercise session, we will employ the same symptoms monitoring system that we used in Active MOMS IRB #24174 and CATS

Symptom Checklist	Pre	5-min	15-min	25-min	Post
Dizziness					
Nausea					
Headache					
Abdominal Pain/Pressure					
Cramping or contractions					
Chest pain					
Calf pain or swelling					
Fluid leakage (urine, amniotic, blood)					
Unusual change in fetal movement					

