10.8 Suspension of research

As outlined above, we will continuously monitor adverse event rates in all participants. The safety officer, together with the study investigators, will alert the IRB and the NIH if a greater than or equal to 20% adverse event rate potentially due to study interventions should occur in the treatment group or if significant differences between treatment groups occur.

Discontinuing subjects from the study. Any subject with a physician-diagnosed serious adverse event related to the study interventions will be discontinued from the study. Should insufficient weight gain be detected and the cause of this weight gain is potentially related to the study interventions as determined by the PIs after consultation with the participant's primary care provider, the participant will be discontinued from the study. Other non-minor concurrent illnesses or major changes in the family social environment would also lead to discontinuation as determined by the investigators alone or in consultation with the PCP.

If a woman experiences a contraindication to exercise in pregnancy that precludes her continued participation, she will be discontinued from the study. These are: Hemodynamically significant heart disease, Restrictive lung disease, Incompetent cervix/cerclage, Persistent second [or third] trimester bleeding, Placenta previa after 26 weeks of gestation, Premature labor during the current pregnancy, Ruptured membranes, Preeclampsia/pregnancy-induced hypertension] per the ACOG guidelines [(2015, December). ACOG Committee opinion. Number 650: Physical Activity and Exercise During Pregnancy and the Postpartum Period. *Obstetrics and Gynecology*, 126,(6), 135-142].

If she experiences a warning sign to continuing exercise (moderate to severe dizziness, nausea, headache, abdominal pain/pressure, cramping or contractions, chest pain, calf pain or swelling, fluid leakage, unusual change in fetal movement; see our protocol for unexpected or AE), she will discontinue or stop exercising, immediately.

Criteria for stopping the trial. It is exceedingly unlikely that any new, outside information will become available during this trial that would necessitate stopping the trial. There are two situations, however, that could potentially necessitate stopping the trial: 1) poor recruitment and/or retention and 2) disparate serious adverse events related to GWG.

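### The exercise-session symptom lists in Sections 6.2.1, 10.8 and 11.0 contradict one another and must be reconciled

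*Combined protocol and SAP*

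**What the plan says.** Three places in the combined protocol and SAP list symptoms that matter during an exercise session.

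- **Section 6.2.1 (Study Procedures)** has a nine-row checklist, asked before exercise, at 5, 15 and 25 minutes, and afterwards, together with a rating of perceived exertion (RPE). It cites ACOG 2015 and is presented as symptom monitoring. Its rows include abdominal pain or pressure, "Unusual change in fetal movement" and "Fluid leakage (urine, amniotic, blood)".
- **Section 10.8 (Suspension of research)** calls a set of symptoms warning signs and says that a woman who has one stops exercising at once. The set includes "abdominal pain/pressure, cramping or contractions, chest pain, calf pain or swelling, fluid leakage, unusual change in fetal movement". The sentence refers the reader to the protocol for unexpected or adverse events.
- **Section 11.0 (Risks)** says "The protocol for unexpected or adverse event during an exercise session is below" and then gives reasons for action under "Symptoms Checklist: Warning Signs to Stop Exercise (ACOG, 2015)". Its nine rows include "Regular painful contractions", "Dyspnea before exercise", muscle weakness after exercise and "Fluid leakage (urine or blood)". An RPE of 15 or higher is printed beside the list as a trigger. The actions follow: stop, make the participant comfortable, call the research center or 911, inform the investigator, complete the event form and adverse-event log, and report to the IRB within 5 weekdays.

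**The concern.** Section 11.0 is the only visible page that joins a list of symptoms to a sequence of actions. A sign absent from its list has no stated route there into the stop, call and report steps. Two of the absent signs are ones for which Section 10.8 orders an immediate stop. Section 10.8 also sends its reader to the adverse-event protocol, and the only in-session one printed here is the Section 11.0 list that lacks them.

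The written list carries weight because of who is in the room. Section 6.2.1 has a research-center nurse present for only part of a business-hours session, and CPR-trained fitness instructors covering sessions after hours. At stake is whether everyone supervising a pregnant participant works from the same reasons to stop.

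**Working it through.** No plan figure needs reproducing. The check sets the three lists side by side.

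| Item | 6.2.1 checklist | 10.8 stop rule | 11.0 action list |
|---|---|---|---|
| Dizziness | yes | yes | yes |
| Nausea | yes | yes | yes |
| Headache | yes | yes | yes |
| Chest pain | yes | yes | yes |
| Calf pain or swelling | yes | yes | yes |
| Contractions | cramping or contractions | cramping or contractions | "Regular painful contractions" |
| Fluid leakage | "Fluid leakage (urine, amniotic, blood)" | leakage, no type given | "Fluid leakage (urine or blood)" |
| Abdominal pain or pressure | yes | yes | **absent** |
| Change in fetal movement | yes | yes | **absent** |
| Dyspnea before exercise | **absent** | **absent** | yes |
| Muscle weakness after exercise | **absent** | **absent** | yes |
| RPE | recorded, no threshold | not mentioned | 15 or higher |

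**Section 6.2.1 against 11.0.** Five rows agree, two are reworded, and two on each side have no counterpart. Each list totals 5 + 2 + 2 = 9 rows. The union is 5 + 2 + 2 + 2 = 11 distinct symptoms, and neither list covers it.

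**Section 10.8 against 11.0.** Of the nine signs in 10.8, five appear unchanged in 11.0, two appear in narrower wording (contractions, leakage) and two do not appear. In the other direction, two symptoms and the RPE trigger in 11.0 are missing from 10.8.

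**Section 6.2.1 against 10.8.** The nine items correspond. The only difference is that 10.8 leaves the type of leakage open.

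**Could damage in the PDF reading explain this?** The trigger line above the Section 11.0 table is scrambled, and the labels on its RPE scale sit on different rows from those in Section 6.2.1. How the RPE trigger combines with the symptoms therefore cannot be read reliably, and the scale labels are not counted as a discrepancy. The symptom rows are another matter: both tables have nine complete rows, and the wording itself differs. Lost text would not turn one contractions row into the other, or add dyspnea and muscle weakness.

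**The case against.** The strongest reply is that the signs are covered. Section 6.2.1 has trained staff ask about all of them at five time points, and Section 10.8 orders an immediate stop without relying on Section 11.0. This stands, and it limits the point in several ways.

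- **A reader might infer that staff would not act on these signs.** The documents do not support that. The gap arises only for staff who rely on the Section 11.0 list alone.
- **A reader might infer that amniotic leakage is a named stop sign elsewhere and was dropped from 11.0.** Only Section 6.2.1 names it, as a monitoring item. Section 10.8 says leakage without a type, which would include it. Section 10.8 also lists ruptured membranes and premature labor as grounds for discontinuing a participant. That is a decision about study participation, though, and not an in-session trigger.
- **The uploaded protocol is not visible.** Sections 10.1 and 20.1 refer to an attached or uploaded adverse-event protocol, which may already be consistent. That would not remove the conflict between the printed Sections 10.8 and 11.0.
- **A reader might take every intervention participant to face this up to four times a week.** Four sessions apply only at the highest step-ups. The baseline level has no supervised exercise session, and the third and fourth sessions may be done at home.
- **A reader might infer that the adverse-event alert is distorted.** Section 10.8 alerts the IRB and NIH at a 20% event rate in the treatment group. With 15 women per group (Section 8.1) that is 0.20 × 15 = 3 women, so a few unrecorded events could matter. But Section 10.2 defines an adverse event broadly and without reference to either checklist, so the documents do not show that events would be missed.

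**Conclusion.** The contradiction is in the current text and holds as an internal inconsistency. Five of nine rows agree between the Section 6.2.1 and 11.0 lists, although both cite the same source. Two signs that Section 10.8 says require an immediate stop have no row in the Section 11.0 list, and two more are worded more narrowly there. Two symptoms and the RPE trigger stand only in 11.0.

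The consequence is bounded: staff using Section 11.0 alone would lack a written trigger for signs that Section 10.8 treats as reasons to stop, while the stop rule in 10.8 remains in force. The conclusion assumes that the symptom rows were read correctly from the PDF. It also assumes that the printed Section 11.0 protocol is meant for use in sessions, as its introduction says. Because these are operative safety instructions for pregnant participants, they should be made consistent even though the plan elsewhere orders the stop.

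**What to change.** Reconcile Sections 6.2.1, 10.8 and 11.0, the session form and the uploaded adverse-event protocol into one symptom checklist and one action list. Have the study's obstetric co-investigator confirm the content, including the wording of the contractions and leakage items and whether an RPE trigger applies. State the list once and have the other sections refer to it. No position is taken here on which list or threshold is right.

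The cost is one amended table, matching cross-references and a reprinted form. Sample size, endpoints and analysis are unaffected.

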12.0 Potential Benefits to Subjects and Others

12.1 Potential Benefits to Subjects

The minimal risks to the participants are greatly outweighed by the benefits of the intervention they receive and the anticipated benefits to themselves and to others if the intervention is shown to be effective. The potential benefit to the participants is greater understanding of healthy behaviors that, if started in pregnancy could positively affect both maternal and fetal short- and long-term health. They will also receive significantly more information on appropriate weight gain in pregnancy, nutrition and healthy eating, self-regulatory behaviors, and psychological health than is usually possible in routine obstetric care. Subjects in the intervention group may achieve better adherence to the Institute of Medicine GWG guidelines (table cited above), which may reduce their risk of hypertension, diabetes, obstetrical complications, and postpartum weight retention.

12.2 Potential Benefits to Others

The benefit of this research to others is the possible development of a novel approach to pregnancy care, which can positively impact maternal/child health in the future, particularly for OW/OB women.

13.0 Sharing Results with Subjects

Subjects will complete HIPAA forms if they want us to share information with their physician; we will share information on their physical activity, healthy eating, weight, goal-setting, and self-monitoring behaviors on a weekly basis as part of the intervention counseling and feedback component. This information will be presented to the participant during the sessions.

14.0 Economic Burden to Subjects

14.1 Costs

None known.

14.2 Compensation for research-related injury

It is the policy of the institution to provide neither financial compensation nor free medical treatment for research-related injury. In the event of injury resulting from this research, medical treatment is available but will be provided at the usual charge. Costs for the treatment of research-related injuries will be charged to subjects or their insurance carriers.

15.0 Number of Subjects

Study 2: target = 30 + anticipated 50 screened failures + 20% dropout (6) + 20 additional control subjects = 106

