1.0 Objectives

1.1 Study Objectives

Purpose: The proposed overall research aims to establish feasibility of delivering an individually-tailored, behavioral intervention to manage gestational weight gain [GWG] that adapts to the unique needs and challenges of overweight/obese pregnant women [OW/OBPW] and will utilize control systems engineering to optimize this intervention; in other words, make this intervention manage GWG in OW/OBPW as effectively and efficiently as possible.

Aim 1: This application is to conduct the second study of the research plan (Study 2) to (a) test an individually-tailored behavioral intervention (including components of physical activity, healthy eating, goal-setting, self-monitoring, and GWG management) with decision rules for when and how to adapt dosages for an individual and (b) the randomization, participant retention, and data collection procedures with an intervention (treatment) and control groups in a cohort of OW/OBPW from approximately ~6-35 weeks gestation; with follow-ups through delivery to 6-weeks postpartum. We hypothesize that women in the intervention group will have more positive eating and activity behaviors and psychosocial and behavioral outcomes as well as manage their GWG better compared to controls.

Aim 2: R56: To prospectively characterize the effects of the intrauterine environment on fetal growth and infant birth weight. Detailed, prospective data collection on Healthy Mom Zone participants offers the novel opportunity to (a) assess how the intrauterine eating and physical activity environment impacts fetal growth and (b) explore the effects of our GWG intervention on fetal growth and infant weight. We hypothesize that by changing the maternal prenatal eating/physical activity environment, a critical time in the lifecycle, we will observe differences between intervention and control mother-infant dyads on in utero markers of fetal growth and

infant birth weight. R56: In addition, we will explore how individual differences in maternal sleep duration, hydration, and stress impact fetal growth and development and infant birth weight.

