3.3 Early Withdrawal of Subjects

3.3.1 Criteria for removal from study

Safety reasons (develops a contraindication to exercise in pregnancy right after recruitment that would exclude her participation from the study; develops a fetal abnormality that requires her to withdrawal from the study per her provider's recommendation)

Failure of subject to adhere to protocol requirements (e.g., not completing assessments and intervention sessions)

Subject withdrawals from study

No returned contact from the subject after recruitment

Pregnancy loss [e.g., miscarriage after recruitment]

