3.3.2 Follow-up for withdrawn subjects

Subjects will be withdrawn from the study based on the criteria listed above. We will make multiple attempts to contact the subjects who fail to return contact after recruitment [our general protocol is to call and email 3 times over a 2-week period, send 1 post card reminder the following week, make 1 additional call and if no contact, the subject is removed from the study] and her data will be coded as loss to follow-up. If a woman is removed for safety reasons, failure to adhere to protocol requirements, or withdraws from the study on her own, we will ask if we are able to continue to follow-up with her for the post-intervention assessments she is willing to complete. If the answer is NO, we will not contact the subject and keep the data that we have collected which will be coded as no follow-up. If the answer is YES, we will maintain protocol contact as applicable (e.g., email/phone) and obtain the appropriate follow-up measures (e.g., completing surveys) and these data will be coded as withdrawal-follow-up.

Subjects will be replaced in study 2 (randomized) according to the randomization scheme. Co-I, [name], HMC, is in charge of the randomization scheme.

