6.2 Study Procedures

6.2.1 STUDY 2 PROCEDURES.

Visit A: Pre-Intervention Assessment. Subject recruitment, screening, and enrollment have been described above. Thirty OW/OBPW who are interested and eligible will be asked to complete a pre-intervention assessment at the Penn State Clinical Research Center to identify the presence of any health issues that may preclude participation in the study. Study women will be carefully screened for medical abnormalities. Women will be escorted to an evaluation room by a project staff member who will then read them a study description, answer questions, and obtain written informed consent. Participants will be given study forms (e.g., where to park, what to do in the event of inclement weather and a session is cancelled, gift card compensation form, etc.; these have been uploaded in the documents section of CATS).

The clinician will assess height, weight, and blood pressure and perform a physical exam to identify health symptoms that may preclude participation (ACOG, 2015 guidelines). The clinician will review the physician consent form and medical history. If no negative health symptoms are present, women will be “cleared” for participation. If any abnormalities or issues are detected (or

health issues that will preclude participation based on the ACOG 2015 guidelines) during the CRC evaluation or baseline assessments we will, with permission of the subject, notify their healthcare provider immediately (or given a referral if she does not have a healthcare provider). We will not proceed with routine study testing if the managing provider deems it inadvisable to continue. All records will be kept with strict confidentiality.

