8.0 Statistical Plan

8.1 Sample size determination

For Study 2, Julios⁵⁰ effectively argues a sample size of 12 per group is adequate to assess feasibility, address regulatory considerations, and obtain sufficient precision of the mean and variance to perform a formal sample size and power calculation for the future RCT. The primary endpoint of the future RCT will be powered on GWG. Factoring in an anticipated 20% subject drop-out based on our pilot work,⁵⁰⁻⁵² we will recruit a total of 30 subjects (i.e., 15 per group).

48. Symons Downs, D. (2011). Determinants and outcomes of physical activity in pregnancy: Findings from Active MOMS, a randomized physical activity intervention for pregnant women. *Annals of Behavioral Medicine*, 41, S135.
50. Julios, S. A. (2005). Sample size of 12 per group rule of thumb for a pilot study. *Pharmaceutical Statistics*, 4, 287-291.

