8.2 Statistical methods

Biostatistician, Co-I [name], will be responsible for coordinating data management and statistical design/analyses aspects required for feasibility studies including data cleaning, analytical set construction, documentation, analyses, and preparation of data summaries for reporting purposes. He will provide leadership in designing/formatting data collection forms to reduce data collection/recording errors and develop a well-defined/comprehensive data quality assurance program to ensure complete, accurate, and valid data, while limiting variability in data collection/recording. Study data will be managed using REDCap (Research Electronic Data Capture), is a secure web application designed to support data capture for research studies, providing user-friendly web-based case reports, real-time data entry validation (data types/range checks) audit trails, and a de-identified data export mechanism to statistical packages (SPSS, SAS, Stata, R/S-Plus). **Analysis Plan.** Study 2 is to establish feasibility; descriptive statistics, including means/standard deviations (continuous variables) and frequencies (categorical variables) will be used to characterize the data. Study 2 will provide estimates for the primary endpoint (GWG) to power a future RCT. Linear mixed-effects models will be used to assess differences between intervention and control groups with respect to changes in continuous outcomes over time (from pre- to post-intervention; daily/weekly) on GWG and related health outcomes. Generalized estimating equations with a logit link will be used to assess differences between intervention and control groups for dichotomous outcomes over time. Because this is a

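### Does the replacement of women who leave (30 + 6 in Section 15) leave retention without a sound denominator?

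*Combined protocol and SAP*

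**What the plan says.** Four parts of the combined protocol and SAP bear on this.

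- **Headcount.** Section 15 gives "Study 2: target = 30 + anticipated 50 screened failures + 20% dropout (6) + 20 additional control subjects = 106". Section 6.2.1 has "Thirty OW/OBPW who are interested and eligible will be asked to complete a pre-intervention assessment", Section 8.1 says "we will recruit a total of 30 subjects (i.e., 15 per group", and Section 16.2 repeats 30.
- **Leaving and replacement.** Among the grounds for removal in Section 3.3.1 is "Failure of subject to adhere to protocol requirements (e.g., not completing assessments and intervention sessions", together with withdrawal, lost contact, safety reasons and pregnancy loss. Section 3.3.2 then states "Subjects will be replaced in study 2 (randomized) according to the randomization scheme" and sets no maximum.
- **Data of women who leave.** Section 3.3.2 gives three follow-up codes: lost to follow-up, no follow-up, and withdrawn but still followed. Even when a woman refuses further contact, the team will "keep the data that we have collected which will be coded as no follow-up".
- **Use of the results.** Aim 1 in Section 1.1 tests "b) the randomization, participant retention, and data collection procedures with an intervention (treatment) and control groups". Section 8.2 says "Study 2 will provide estimates for the primary endpoint (GWG) to power a future RCT" and treats drop-out as information for reducing missing data in that trial. Section 10.8 lists poor retention among the situations that could stop the study.

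No section defines a retention rate, its denominator, or an analysis set.

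**The concern.** Replacement and retention pull against each other. Women removed for non-adherence, withdrawal or lost contact are retention failures, and they are also women whom Section 3.3.2 replaces. If retention were counted on the 30 places as finally filled, it would come out near 100% however many women had been lost and replaced.

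An over-optimistic figure could mislead the later trial. As an illustration, assume that trial needs 100 completers. It would recruit 100/0.80 = 125 women at 80% retention, but only 100/0.96 = 104.2 at 96%, or 100 at 100%. With a true loss of 20%, the last two would leave 104.2 × 0.80 = 83.3 and 100 × 0.80 = 80 completers.

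The gestational weight gain (GWG) estimates raise the same question. Leaving replaced women out of the models would tend to select those who adhered. The unlabelled six in Section 15, set against 30 elsewhere, adds to the impression that nobody has settled how many women count.

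**Working it through.** **The plan's own figures**

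- Section 8.1: 12 per group with 20% drop-out gives 12/(1 − 0.20) = 15 per group, 30 in total. This reproduces.
- Section 15: 0.20 × 30 = 6, and 30 + 50 + 6 + 20 = 106. This also reproduces.
- The 30 already contains the 20% allowance, as Section 8.2 confirms when it says the sample was inflated. The six are therefore either replacements under Section 3.3.2 or a second allowance for the same loss. On the first reading 36 overweight or obese women are planned and the total is 106. On the second the total would be 106 − 6 = 100.
- The target does not depend on the answer: 30 − 6 = 24 women, or 12 per group, is what Section 8.1 asks for before any replacement.

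**Retention under each denominator**

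Inputs: 20% loss among the first 30 (Section 8.1) and six replacements (Section 15). The loss among replacements is not given, so it is taken as 20% or none. Intervals are exact 95%.

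| Denominator | Replacements also lose 20% | No replacement lost |
|---|---|---|
| First 30 | 24/30 = 80.0% (61.4 to 92.3) | same |
| All 36 randomised | (24 + 4.8)/36 = 80.0% | 30/36 = 83.3% (67.2 to 93.6) |
| 30 filled places | 28.8/30 = 96.0% | 30/30 = 100% (88.4 to 100) |

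The first two rows differ by at most 83.3 − 80.0 = 3.3 points. The interval for 24/30 is 92.3 − 61.4 = 30.9 points wide, so the choice between those two rows is small beside sampling error. Only the third row misleads, by 100 − 83.3 = 16.7 points or 96.0 − 80.0 = 16.0 points.

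**Does the text lead to the third row?**

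- Section 3.3.2 retains leavers' data under separate follow-up codes. Those codes would serve little purpose if leavers dropped out of the count.
- Section 8.2 compares women with and without missing data and looks for reasons for drop-out. Neither can be done on filled places alone.
- Section 10.4 provides for a periodic report on discontinued subjects.
- Section 15 itself describes the six as drop-out.
- For GWG, no section excludes replaced women, and the linear mixed models in Section 8.2 can use whatever weights each woman contributed.

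**The case for a change.** The strongest case for a change is that the plan never commits itself. Retention is a named aim, Section 10.8 makes it a possible reason to stop without giving a threshold, and a woman who withdraws but agrees to follow-up may supply post-intervention data alongside her replacement. Two sentences in Section 8.2 would settle this at almost no cost.

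The omission is real, and so is the unexplained overlap between the 20% inside the 30 and the six added in Section 15. A statistician writing the report should show the flow of all randomised women by arm, with reasons for leaving.

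The rest is weaker:

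- The shortfall in a later trial rests on a use that the plan does not state. The sizing input that Sections 8.1 and 8.2 name is GWG. Drop-out is to be studied for its causes and prevention.
- A rule that every replaced woman counts as not retained would mix pregnancy loss and safety removals with attrition. It would also count as lost some women whom Section 3.3.2 continues to follow.
- A stated maximum of 36 would add a limit that Section 3.3.2 does not contain.
- The size of the gap depends on the loss. Section 16.2 reports under 5% drop-out in an earlier trial. At 5%, 1.5 women in 30 leave, and if all are replaced and no replacement is lost, 30/31.5 = 95.2% stands against 100%, a gap of 4.8 points.

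**Conclusion.** No change to the plan follows. It leaves a definition unwritten, but nothing in it points to the one misleading choice and several provisions point away from it. An analyst following Sections 3.3.2 and 8.2 would report all randomised women and use their available weights. The reasonable denominators then differ by at most 3.3 points, in a study whose 95% interval for retention spans about 31 points and which Section 8.2 describes as not powered for firm conclusions.

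The six in Section 15 is a labelling slip in an administrative count that also includes 50 screen failures. Whether the total is 106 or 100, the 12-per-group target and the planned models stay the same.

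This rests on three assumptions: the 20% loss in Section 8.1, six replacements as in Section 15, and replacement losses between none and 20%. Part of the monitoring section, between 10.4 and 10.6, was not available to check. The conclusion would differ if a report counted retention on filled places or dropped replaced women from the GWG models, but the documents propose neither.
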